Baseline blood work may NOT be collected before obtaining informed consent if the following criterion is met:

1. Baseline blood work required to confirm eligibility according to study protocol SBI-CIP 20-002 is NOT performed as part of the site's standard of care for all patients undergoing breast conserving surgery.

The participant's weight will be collected ≤ 7 days prior to administration of the study drug and recorded on the eCRF and communicated to an unblinded qualified medical professional (e.g.

SBI-CIP Rev: 20-002 v1.8	A prospective multi-center clinical study evaluating the use of PD G 506 A and the Eagle V1.2 Imaging System for the visualization of carcinoma during breast conserving surgery	Page: 66 of 157
--	--	-----------------

pharmacist) responsible for preparing and dispensing the investigational drug or placebo (Sections 10.1.2.3, 10.1.2.4, 10.1.2.5). Diagnostic imaging may be performed ≤ 90 days prior to administration of the study drug. Diagnostic histopathology may be performed ≤ 90 days prior to administration of the study drug.

Consented patients will be asked to complete the pre-operative Breast Conserving Therapy Module of the Breast-Q survey to establish their baseline score. Patients may complete this survey anytime between Day -30 and Day 1 (day of surgery).

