15.7. Secondary and Exploratory Endpoint Analysis

Secondary and exploratory endpoints based on *patient-level* data will be analyzed using similar methods to the primary and key secondary endpoints, using Wilson (score) confidence intervals. Re-operation rates will be compared between treatments using Fisher's exact tests.

Secondary and exploratory endpoints based on *orientation-level, primary specimen-level, and point-level* data will be analyzed using a weighted estimator, proposed by Lee and Dubin (Lee and Dubin, 1994), which takes into account the correlation (clustering) of the margins within a patient. This method will be used to calculate the estimates and two-sided 95% confidence intervals.

Descriptive statistics will be used to summarize the weight of resected tissue specimens (SoC specimens vs. FGR specimens). Mean total tissue weight (Arm 1 vs. Arm 2) will be compared using a two-sample t-test.

Breast-Q survey results will be summarized using actual values and change from baseline values using descriptive statistics. The difference in change scores between Arm 1 and Arm 2 will be summarized descriptively and presented along with a 95% confidence interval on the difference in means. For the Breast-Q survey results at 3 months, if the lower bound of this confidence interval is \geq - 10 then non-inferiority will be claimed. Results at 6 months and 1 year will be described with summary statistics. For the analysis of Breast-Q survey results, the previously defined minimal important difference as the reference point for what patients consider a meaningful change in Breast-Q scores. The minimal important difference is defined as: "The smallest difference in score in a domain of interest that patients perceive as beneficial and which would mandate, in the

|--|

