Appendix 6. Breast-Q Version 2.0 © - Breast Conserving Therapy Module

BREAST-QTM - BREAST CANCER CORE SCALE (PREOPERATIVE) VERSION 2.0: SATISFACTION WITH BREASTS

With your breast area in mind, in the past week, how satisfied or dissatisfied have you been with:

		Very Dissatisfied	Somewhat Dissatisfied	Somewhat Satisfied	Very Satisfied
a.	How you look in the mirror clothed ?	1	2	3	4
b.	How comfortably your bras fit?	1	2	3	4
c.	Being able to wear clothing that is more fitted?	1	2	3	4
d.	How you look in the mirror unclothed ?	1	2	3	4

BREAST-Q VERSION 2.0 © Memorial Sloan Kettering Cancer Center and The University of British Columbia, 2017. All rights reserved.

SBI-CIP 20-002	Rev: v1.8	A prospective multi-center clinical study evaluating the use of PD G 506 A and the Eagle V1.2 Imaging System for the visualization of carcinoma during breast conserving surgery	Page: 141 of 157
-----------------------	--------------	--	------------------

BREAST-QTM-BCT MODULE (POSTOPERATIVE) VERSION 2.0: SATISFACTION WITH BREASTS

The following questions are about your breasts and your breast cancer treatment (by treatment, we mean lumpectomy with or without radiation). If you have had a lumpectomy and radiation of both breasts, answer these questions thinking of the breast on which the study procedure was performed. If you are unsure on which breast the study procedure was performed, ask your surgeon. With your breasts in mind, in the past week, how satisfied or dissatisfied have you been with:

		Very Dissatisfied	Somewhat Dissatisfied	Somewhat Satisfied	Very Satisfied
a.	How you look in the mirror clothed ?	1	2	3	4
b.	The shape of your lumpectomy breast when you are wearing a bra?	1	2	3	4
c.	How normal you feel in your clothes?	1	2	3	4
d.	Being able to wear clothing that is more fitted?	1	2	3	4
e.	How your lumpectomy breast sits/hangs?	1	2	3	4
f.	How smoothly shaped your lumpectomy breast looks?	1	2	3	4
g.	The contour (outline) of your lumpectomy breast?	1	2	3	4
h.	How equal in size your breasts are to each other?	1	2	3	4
i.	How normal your lumpectomy breast looks?	1	2	3	4
j.	How much your breasts look the same?	1	2	3	4
k.	How you look in the mirror unclothed?	1	2	3	4

BREAST-Q® VERSION 2.0 © Memorial Sloan Kettering Cancer Center and The University of British Columbia, 2017. All rights reserved.

|--|

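### The 3-month Breast-Q non-inferiority comparison uses an unadjusted change score across two different forms; adjusting the post-operative score for baseline would be more precise at no cost

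*Combined protocol and SAP*

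**What the plan says.** Section 15.7 states that "Breast-Q survey results will be summarized using actual values and change from baseline values using descriptive statistics". It then takes the difference between arms in mean change, with a 95% confidence interval, and claims non-inferiority at 3 months if the lower bound is at or above -10. It names no covariate. Endpoint P(2.18) in Section 7.2.2 is also framed as scores before and after surgery.

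The baseline comes from Section 12.2: "Consented patients will be asked to complete the pre-operative Breast Conserving Therapy Module of the Breast-Q survey to establish their baseline score". The 3-month score comes from the post-operative module (Section 12.8).

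Appendix 6 prints both forms. The baseline form is titled "BREAST CANCER CORE SCALE (PREOPERATIVE) VERSION 2.0: SATISFACTION WITH BREASTS" and has 4 items (a to d). The follow-up form is the BCT "MODULE (POSTOPERATIVE) VERSION 2.0: SATISFACTION WITH BREASTS" and has 11 items (a to k). All items are scored 1 to 4.

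Later in Section 15.7 the margin is stated again, this time as a mean difference in change at or below -10, taken as Arm 1 minus Arm 2. Section 15.2 sizes Part B on P(1.1) alone. No SD, pre-post correlation, power or scoring rule is given for Breast-Q, and Section 15.1 leaves further analysis detail to the SAP.

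**The concern.** A change score is easiest to defend when the same instrument is used at both times and the two scores are strongly related. Here the instrument changes between baseline and follow-up. If the pre-operative score is only weakly related to the post-operative one, subtracting it carries its variability into the outcome.

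Comparing patient-reported cosmetic outcome is one of the stated purposes of Arm 1 (Section 8.1 and Appendix 1). Arm 1 has only about 72 patients, and that small arm limits the precision of the comparison. At stake are the width of the interval that is set against the 10-point margin, and the meaning of the within-arm change summaries, which mix any real change in satisfaction with a change of questionnaire.

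**Working it through.** **Step 1. Compare the forms (Appendix 6).** Three items have the same wording on both: appearance in the mirror clothed, appearance in the mirror unclothed, and "Being able to wear clothing that is more fitted". The fourth baseline item, "How comfortably your bras fit", has no identical follow-up item. Eight of the 11 follow-up items have no identical baseline item, for example "How much your breasts look the same". Five of them (b, e, f, g, i) name the lumpectomy breast.

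**Step 2. Arm sizes (Section 15.2).** The plan gives no Breast-Q calculation to reproduce, but its arm sizes do reproduce from P(1.1):

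n = ((1.960 × √(0.01 × 0.99) + 1.2816 × √(0.03 × 0.97)) / 0.02)² = 427.7, so 428 in Arm 2.

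428 × 7/6 = 499.3, so 500 in total and 72 in Arm 1. These are the numbers before the 5% loss allowance is added.

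**Step 3. Variance.** Let s be the SD at both times and r the pre-post correlation. Both are assumptions.

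- Change score: SD = s√(2(1 - r))
- Baseline-adjusted (ANCOVA): SD = s√(1 - r²)
- Variance ratio: 2(1 - r)/(1 - r²) = 2/(1 + r)

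With unequal SDs s_pre and s_post, the change-score variance exceeds the ANCOVA variance by (s_pre - r·s_post)², which is never negative. So the direction of the result does not depend on equal SDs; its size does.

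**Step 4. Half-widths at s = 20.** SE = SD × √(1/72 + 1/428) = SD × 0.1274, and half-width = 1.96 × SE.

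| r | Change score | ANCOVA | Variance ratio |
|---|---|---|---|
| 0.2 | 6.3 | 4.9 | 1.67 |
| 0.3 | 5.9 | 4.8 | 1.54 |
| 0.5 | 5.0 | 4.3 | 1.33 |
| 0.7 | 3.9 | 3.6 | 1.18 |

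**Step 5. Power for the 10-point margin at a true difference of 0.** Power = Φ(10/SE - 1.96).

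| s | r | Change score | ANCOVA |
|---|---|---|---|
| 15 | 0.3 | 99% | about 100% |
| 20 | 0.3 | 91% | 98% |
| 20 | 0.5 | 97.5% | 99.5% |
| 25 | 0.3 | 76% | 91% |

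**Step 6. Against the unadjusted 3-month score.** The variance ratio is 2(1 - r): 1.6 at r = 0.2, 1.4 at 0.3, 1.0 at 0.5 and 0.6 at 0.7. Against this comparator the change score loses only when r is below 0.5.

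**Step 7. Direction of the margin.** With Arm 1 minus Arm 2, a worse result in Arm 2 makes the difference positive. A lower bound at or above -10 then puts no limit on harm in Arm 2, and a difference at or below -10 would mean that Arm 2 did better by at least 10 points. The two statements in Section 15.7 cannot both be the rule.

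**The case against.** **The ratio 2/(1 + r) is generic.** It would apply with one identical form at both visits. This stands: the mismatch enters only through a lower r, which is plausible but not documented. A reader might attribute the whole precision loss to the mismatch, and the documents do not support that.

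**The arm comparison is valid as planned.** This stands. Randomisation gives both arms the same expected baseline, so the subtraction does not bias the difference. A wider interval makes non-inferiority harder to claim, so a reader who inferred a risk of a false claim from the mismatch would be wrong.

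**The practical effect is small.** Largely true. Even the widest half-width in the table, 6.3, lies inside the 10-point margin, and at SD 15 to 20 with r of 0.3 or more the change score keeps at least about 91% power. Only a larger SD with a low r makes the loss material. The endpoint is outside the primary and key secondary tests (Section 15.6).

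**Some tempting additions fail.** One could infer that raw totals, 4 to 16 and 11 to 44, will be subtracted. That is implausible beside a cited minimal important difference of 7 to 8 points; what is missing is a stated scoring rule. One could also say that Section 12.2 names the wrong form, but the heading of Appendix 6 places both forms under the Breast Conserving Therapy Module. And the lack of an 11-item baseline is partly inherent, since items about the lumpectomy breast cannot be asked before lumpectomy.

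**Detail is deferred to the SAP.** Section 15.7 has already chosen the change score, so the deferral does not settle the point.

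**Conclusion.** The point holds as a minor one. Baseline and follow-up are different forms with three shared items, and the planned non-inferiority analysis is an unadjusted difference in change between them. A baseline-adjusted comparison of the same data is more precise. Under an assumed SD of 20 and 72 v 428 patients, the half-width falls from 6.3 to 4.9 points at r = 0.2 and from 3.9 to 3.6 at r = 0.7. The power gain is modest at SD 15 to 20 and material at SD 25 with r = 0.3 (76% v 91%). These sizes rest on an assumed SD, an assumed r, equal SDs and complete 3-month data.

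The documents do not support a reading that the arm comparison is biased or the non-inferiority test invalid because of the two forms. What the change of form does damage is the within-arm change from baseline, which has no clear meaning without a common metric. The conflicting margin statements are a separate defect in the same rule and must be resolved before any 10-point criterion can be applied.

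**What to change.** In Section 15.7:

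- Compare the 3-month post-operative score between arms by ANCOVA, with the pre-operative score and the cancer-type randomisation stratum (Section 8.1) as covariates. ANCOVA does not need the two forms on one metric. Under randomisation it targets the same arm difference as the change score, so the 10-point margin carries over.
- State the rule once: adjusted difference Arm 2 minus Arm 1, non-inferiority if the lower 95% bound is at or above -10. Reconcile the later Arm 1 minus Arm 2 wording with it.
- Report pre- and post-operative scores separately instead of within-arm change, and state how each form is scored.
- Align the before-and-after wording of P(2.18) in Section 7.2.2.

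The cost is wording in the protocol and SAP. Both forms are already collected, and no visit, item or patient is added.

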8.1. Description of the Study Design

This pivotal study is a 2-part, double -blind (pathologist(s) & patient – blinded) randomized placebo-controlled trial (Arm 1: placebo + SoC BCS, Arm 2: SoC BCS + Eagle V1.2 Imaging System + PD G 506 A) to evaluate the *patient-level* clinical usefulness, as well as *patient-* and *orientation-level* diagnostic performance and safety of PD G 506 A-induced fluorescence for the real-time visualization of carcinoma missed by SoC lumpectomy for breast cancer. Part A is an open-label training phase of the study to optimize workflow and train *surgeon's* and *surgeon's* assistant on the day 1 study-specific procedures; Part B of the study is randomized and double -blind and will serve as the pivotal portion of the study. The Eagle V1.2 Imaging System will be used for the visualization of fluorescence. SBI ALApharma Canada requires completion of the Investigator Training Program to ensure the controlled distribution and safe use of PD G 506 A investigational drug and the Eagle V1.2 Imaging System investigational medical device to trained surgeons for use in clinical trials.

Part A will not be randomized; all participants in Part A will receive PD G 506 A. The Day 1 procedures for Part A patients will be carried out with support and oversight from the Sponsor. Part A will include approximately 75 patients. Data acquired from the first 30 patients in Part A will be used to optimize the study workflow and to confirm the sample size for Part B. The remaining approximately 45 patients on Part A will be allocated to training for *surgeon's* and *surgeon's* assistants prior to their enrolling patients into Part B. All *surgeon's* and *surgeon's* assistants must complete at least 1 procedure in Part A, before enrolling a patient into Part B. A given site can only be enrolling patients for either Part A or Part B at any given time. In the event a new *surgeon* is brought onto the study after the site has begun enrolling patients into Part B, they must shadow a study surgeon for at least one Arm 2 patient procedure. In the event a new *surgeon's assistant* is brought onto the study after the site has begun enrolling patients into Part B, they must shadow a study surgeon assistant for at least one patient procedure before participating in as the *surgeon's assistant*.

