Only data from participants in Part B will be used for the analyses of primary and secondary efficacy. Data from all participants in both Part A and Part B will be used for the evaluation of safety.

In Part B of the study, participants will be randomized in a ratio of 1:6 (Arm 1 [SoC]: Arm 2 [PD G 506 A]).

The randomization will be stratified by breast cancer type (invasive carcinoma with or without in situ carcinoma vs. in situ carcinoma alone). This will ensure an approximate ratio of 1:6 within each type of breast cancer. Preoperative diagnosis based on diagnostic tissue sampling performed during screening (e.g. percutaneous core needle biopsy, fine-needle aspiration cytology) will be

SBI-CIP 20-002 Rev: v1.8 A prospective multi-center clinical study evaluating the use of PD G 506 A and the Eagle V1.2 Imaging System for the visualization of carcinoma during breast conserving surgery	Page: 46 of 157
---	-----------------

used for stratification. Permuted blocks will be used to construct the randomization schedule and the randomization will be implemented using an interactive web response system.

Data from the SoC arm (Arm 1) will not be used for statistical analysis of the primary and most secondary endpoints. The purpose of the SoC arm is to compare resected tissue weight, patient reported cosmetic outcomes, re-excision prior to initiation of adjuvant therapies, re-excision within 1-year of index BCS, and safety between study arms as well as to minimize bias introduced into the SoC procedure if the *surgeon* is aware that they have an opportunity to revise the margins further after SoC is complete. A 3-month, 6-month and 1-year follow-up will be performed to evaluate patient reported cosmetic outcomes as well as the rate of re-excision across both study arms. The 6-month and 1-year follow-up data will be collected as an extension phase to the study, meaning database lock and analysis of all other endpoints will be performed following the last patient's 3-month follow-up data is collected. Analysis of 6-month and 1-year data will occur after the last patients 1-year visit. The clinical study report will be appended to include the 6-month and 1-year data, when available.

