15.6. Primary and Key Secondary Endpoint Analyses

There is one primary endpoint and three co-key secondary endpoints for this study: P(1.1), P(2.1), P(2.2) and P(2.3) See Section 7 for the formulas used. These four endpoints will each be tested at the 0.05 level. Only the primary efficacy endpoint test must be significant for the study to be considered positive. Information on the analyses and hypotheses are provided below.

15.6.1. Primary Endpoint:

1. P(1.1): Conversion Rate Among All Patients

The primary endpoint, P(1.1), is the percentage of participants with negative-margins following FGR among all patients following SoC. Participants that are converted from margin-positive after SoC to margin-negative after FGR will be considered a 'clinical success' and will be counted towards the numerator of the primary endpoint. If at the completion of Eagle V1.2 Imaging System assessment red PpIX FL is still observed on the *final margins after FGR* and/or in the *surgical cavity* and no further resection is performed, the anatomical surface(s) of residual fluorescence (i.e., S, M, P, L, I, A) and the reason for not performing further *FGR* is recorded. In such cases, orientation(s) involving FL observed in the *final margin after FGR* and/or in the *surgical cavity* will *not* contribute to the determination of a histopathologically-negative final margin for this primary endpoint.

Participants that are margin-positive after SoC and remain margin-positive after FGR will be considered a 'clinical failure' and will be counted towards the denominator of the primary endpoint proportion. See Section 7.1 for the formula.

The number and percentage of patients with negative-margins following FGR among patients with positive margins following SoC will be provided along with a two-sided 95% confidence interval calculated using the Wilson (score) method. The analysis will be performed using the mITT population.

The statistical hypothesis is as follows: H_0 : $P(1.1) \le 1\%$ vs $H_a = P(1.1) > 1\%$

If the lower bound of the Wilson (score) confidence interval is above 1%, the endpoint will be assumed to be statistically significant. The result is expected to be >3%.

SBI-CIP 20-002 Rev: v1.8 A prospective multi-center clinical study evaluating the use of PD G 506 A and the Eagle V1.2 Imaging System for the visualization of carcinoma during breast conserving surgery Page: 103 of 1	5 7
---	------------

15.6.2. Key Secondary Endpoints:

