absence of troublesome side effects and excessive cost, a change in the patient's (health care) management''⁷⁰. While patients in Arm 2 are anticipated to have marginally more tissue removed as a result of *FGR* as compared to SoC [analyzed in secondary endpoint P(2.16)], it is not anticipated that resection of this additional tissue will negatively affect the patient's satisfaction with the appearance of their breasts as compared to patients in Arm 1. For secondary endpoint 18 [P(2.18a) & P(2.18b)] we have defined a mean difference in change score \leq -10 (Arm 1 – Arm 2) as meeting our criterion for non-inferiority. Previous studies have reported a minimal important difference in Breast-Q scores of 7-8⁷¹ for the breast satisfaction subscale in breast reconstruction patients. To date there are no known publications addressing the minimal important difference using the Breast Conserving Therapy module of the Breast-Q survey. While a change score of \geq -10 would represent a negative change in breast satisfaction, this risk may still be considered acceptable to patients if the intervention is associated with improved clinical outcomes (e.g. decreased probability of having positive margins).

Depth of tumor analyses of tissue specimens identified by FL imaging will be summarized using descriptive statistics.

Exploratory subgroup analyses will be performed on key efficacy endpoints. Subgroups will include patients who underwent sentinel node mapping with blue dye injection vs. those who did not, and patients who underwent comprehensive circumferential shaves during surgery vs. those who had selective shaves during BCS.

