Objectives: This Phase 3 study will evaluate the safety and *patient-level* clinical usefulness, as well as *patient* and *orientation-level* diagnostic performance of PD G 506 A (ALA HCl granules for oral solution)-induced fluorescence for the real-time detection of carcinoma during standard of care (SoC) BCS. *Orientation-level* analyses are based on the fluorescence and carcinoma status of the *primary specimen*, *cavity shave specimens* removed during resection, and the fluorescence status of the *final cavity after FGR*.

carcinoma during breast conserving surgery	SBI-CIP 20-002	Rev: v1.8	A prospective multi-center clinical study evaluating the use of PD G 506 A and the Eagle V1.2 Imaging System for the visualization of carcinoma during breast conserving surgery	Page: 116 of 157
--	-----------------------	--------------	--	------------------

Overall Design: Protocol SBI-CIP 20-002 is a 2-part, double -blind [pathologist(s) & patients -blinded] randomized placebo-controlled trial (Arm 1: SoC BCS, Arm 2: SoC BCS + Eagle V1.2 Imaging System + PD G 506 A) to evaluate the safety and *patient-level* clinical usefulness, as well as *patient-* and *orientation-level* diagnostic performance of PD G 506 A-induced fluorescence for the real-time visualization of malignant tissue(s) during SoC lumpectomy for breast cancer. Part A is an open-label training phase of the study to optimize workflow and Part B of the study is randomized and double-blind and will serve as the pivotal portion of the study.

The Eagle V1.2 Imaging System will be used for the visualization of fluorescence. Data from the SoC arm will not be used for statistical analysis of the primary and key secondary efficacy endpoints. The purpose of the SoC arm is to compare patient reported cosmetic outcomes between study arms as well as to minimize bias introduced into the SoC procedure if the study *surgeon* is aware that they have an opportunity to revise the margins further after SoC is completed.

Number of Patients: The sample size of Part A has been chosen on pragmatic grounds to be approximately 75 patients. Part A will include 75 patients assigned to receive PD G 506 A and undergo SoC BCS followed by FGR. The sample size for Part B will be determined based on the results of the first 30 Part A patients' data.

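### Section 15.7 gives two incompatible Breast-Q non-inferiority rules: one is met only if the FGR arm looks at least 10 points better, and the other does not say which arm is subtracted from which

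*Combined protocol and SAP*

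**What the plan says.** Section 15.7 deals with satisfaction with breasts (secondary endpoint 18, P(2.18a) and P(2.18b)) in two consecutive paragraphs.

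- **Confidence-limit rule.** "The difference in change scores between Arm 1 and Arm 2 will be summarized descriptively and presented along with a 95% confidence interval". At 3 months, if the lower limit is ≥ minus "10 then non-inferiority will be claimed". The order of subtraction is not stated.
- **Point-estimate rule.** For the same endpoint, the sponsor takes a mean difference in change score ≤ minus "10 (Arm 1 – Arm 2) as meeting our criterion for non-inferiority". No confidence limit is mentioned.
- **Rationale.** A change score of ≥ −10 "would represent a negative change in breast satisfaction, this risk may still be considered acceptable to patients", provided clinical outcomes improve. Here −10 is a tolerable loss.

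Section 8.1 identifies the arms: "Arm 1: placebo + SoC BCS", with Arm 2 receiving PD G 506 A and fluorescence-guided resection (FGR). The response options in Appendix 6 run from 1 (very dissatisfied) to 4 (very satisfied), so higher is better.

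**The concern.** A non-inferiority rule should limit how much worse the FGR arm could be. With the order it prints, the point-estimate rule instead requires FGR to look clearly better. The confidence-limit rule is a proper non-inferiority rule in one order of subtraction and runs backwards in the other, and the plan does not say which order applies.

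This comparison is a main reason for having a control arm. Section 8.1 says "The purpose of the SoC arm is to compare resected tissue weight, patient reported cosmetic outcomes" and other outcomes, and the synopsis says "The purpose of the SoC arm is to compare patient reported cosmetic outcomes between study arms". The rule is also the only formal criterion for the claim that removing extra tissue does not harm cosmetic outcome. As printed, the same result can be non-inferior under one sentence and not under the next, and the protocol does not fix the direction before the data are seen.

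**Working it through.** The plan gives no sample size, power or SD for this claim, so there is no figure to reproduce. The check is sign algebra, followed by an illustration of size.

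**Inputs from the plan.** Margin −10 and both rules (15.7); Arm 1 = standard of care (8.1); higher = more satisfied (Appendix 6); 72 and 428 patients (15.2).

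**Assumed inputs.** SD of the change score 15, 20 or 25, in the same points as the margin; survey return 60% to 100%. The plan gives neither.

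Let D = observed mean change in Arm 2 minus that in Arm 1, so positive D favours FGR. Let SE be its standard error.

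**Step 1. Point-estimate rule.** Arm 1 − Arm 2 ≤ −10 is the same as D ≥ +10. It is met only if FGR is observed at least 10 points better.

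**Step 2. Confidence-limit rule, both orders.**

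- (a) Arm 1 − Arm 2, the only order printed: −D − 1.96·SE ≥ −10, so D ≤ 10 − 1.96·SE. The point-estimate rule needs D ≥ 10. For any SE > 0 no data set meets both. This version caps how much better FGR may be and never limits how much worse.
- (b) Arm 2 − Arm 1, the order the rationale implies: D − 1.96·SE ≥ −10, so D ≥ −10 + 1.96·SE. This is the standard rule, and only the point-estimate rule is then wrong.

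**Step 3. Size.** SE = SD × √(1/72 + 1/428) = SD × 0.1274, which gives 1.91, 2.55 and 3.18 for SD 15, 20 and 25. At 60% return, SE is divided by √0.6; the largest value is 3.184/0.7746 = 4.11.

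Chance of meeting each rule (normal approximation, SD 20, full return):

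| True D | Confidence limit, (b) Arm 2 − Arm 1 | Confidence limit, (a) Arm 1 − Arm 2 | Point estimate |
|---|---|---|---|
| −10 | 2.5% | about 100% | about 0% |
| 0 | 97.5% | 97.5% | 0.004% |
| +10 | about 100% | 2.5% | 50% |

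The entries for equal arms are Φ(10/2.548 − 1.96) = 97.5% and Φ(−10/2.548) = 0.004%.

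Over SD 15 to 25 and return 60% to 100%:

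- Point-estimate rule, equal arms: at most 0.08% at full return (SD 25), and at most Φ(−10/4.11) = 0.75% at 60% return.
- Confidence-limit rule, order (b), equal arms: from Φ(10/4.11 − 1.96) = 68% to 99.95%. If FGR is truly 10 points worse, 2.5%.
- Confidence-limit rule, order (a), FGR truly 10 points worse: at least Φ(20/4.11 − 1.96) = 99.8%.

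**Step 4. Where the rules disagree under (b).** At SD 20 and full return the confidence-limit rule needs D ≥ −10 + 1.96 × 2.548 = −5.0, while the point-estimate rule needs D ≥ +10. Every observed result from 5.0 points worse to just under 10 points better passes the first and fails the second. The lower end is −10 + 1.96 × 1.91 = −6.3 at the smallest SE and −10 + 1.96 × 4.11 = −1.9 at the largest.

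**The case against.** The strongest reply is that the intent is clear. The confidence-limit sentence is the operative rule, the rationale treats −10 as a tolerable loss, and together they point to Arm 2 − Arm 1. The other sentence may only carry a stray minus sign: Arm 1 − Arm 2 ≤ +10 runs in a valid direction. I agree that (b) is the likelier intent, but the printed rule is still wrong. Even with that sign corrected it would rest on a point estimate, which is met 50% of the time when FGR is truly 10 points worse, against 2.5% for the confidence limit.

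The inequality sign could have been misread from the PDF. If it were ≥, the two rules would no longer exclude each other under (a), but Arm 1 − Arm 2 ≥ −10 means D ≤ +10, which still puts no limit on harm to the FGR arm.

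Two further points stand as limits. Appendix 6 shows only items scored 1 to 4 and no conversion to a total score, so the assumed SDs are illustrative. And section 15.1 leaves further detail to the SAP, so what can be said is that the protocol does not fix the direction, not that anyone would choose it after the fact. A SAP could not, however, follow both sentences.

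**Conclusion.** The concern holds. The two rules for one claim are incompatible under either order of subtraction. The point-estimate rule demands an observed FGR advantage of at least 10 points, against its own rationale. These conclusions rest only on the printed rules, the identity of the arms and the direction of the score.

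The probabilities depend on the assumed SD and return rate, but the contrast is large throughout: with truly equal arms, the point-estimate rule is met in under 1% of trials and the confidence-limit rule, read as Arm 2 − Arm 1, in 68% to 99.95%.

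The consequence is limited to a secondary endpoint. Section 15.2 sizes Part B on P(1.1) alone, and section 15.6 says "Only the primary efficacy endpoint test must be significant for the study to be considered positive". It should be fixed, but it does not threaten the trial's main conclusion.

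**What to change.** In section 15.7, replace the confidence-limit sentence with one complete rule:

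> *The difference in mean change from baseline at 3 months is defined as Arm 2 − Arm 1. Non-inferiority is claimed only if the lower limit of the two-sided 95% confidence interval is above −10.*

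This keeps the sponsor's margin; keeping the printed ≥ in place of above makes no practical difference. Delete the sentence that sets the criterion at ≤ −10 for Arm 1 − Arm 2. State the same Arm 2 − Arm 1 direction in the sentence about an acceptable negative change, and carry the same wording into the SAP. The change costs wording only: no extra patients, data or visits.
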